9.2.1.1. Response Categories

Disease evaluations must be performed every 28 days for the first 2 years and then every 8 weeks until disease progression (or other reasons as per Section 10). A window of ± 7 days is allowed. If treatment has been delayed for any reason, the disease evaluations must be performed according to schedule, regardless of any changes to the dosing regimen.

Disease evaluations will be performed by a central laboratory (unless otherwise specified). This study will use the IMWG consensus recommendations for multiple myeloma treatment response

criteria (Durie 2006, Rajkumar 2011)^{7,32} presented in Table 8. For quantitative immunoglobulin, M-protein, and immunofixation measurements in serum and 24-hour urine, the investigator will use results provided by the central laboratory. Subjects with positive serum IFE and confirmed daratumumab IFE interference, that meet all other clinical criteria for complete response or stringent complete response, will be considered CR/sCR.

Disease progression must be consistently documented across clinical study sites using the criteria in Table 8. For patients with measurable disease by SPEP or UPEP at baseline, increases in serum free light chains (FLC) or the FLC ratio alone do not meet criteria for progressive disease.

Table 8: International Uniform Response Criteria Consensus Recommendations

Response	Response Criteria	
Stringent complete Response (sCR)	 CR as defined below, plus Normal FLC ratio, and Absence of clonal PCs by immunohistochemistry, immunofluorescence^a or 2 to 4 color flow cytometry 	
Complete response (CR)*	 Negative immunofixation on the serum and urine, and Disappearance of any soft tissue plasmacytomas, and <5% PCs in bone marrow 	
Very good partial Response (VGPR)*	 Serum and urine M component detectable by immunofixation but not on electrophoresis, or ≥90% reduction in serum M protein plus urine M protein <100 mg/24 hours 	
Partial response (PR)	 ≥50% reduction of serum M protein and reduction in 24 hour urinary M protein by ≥90% or to <200 mg/24 hours If the serum and urine M protein are not measurable, a decrease of ≥50% in the difference between involved and uninvolved FLC levels is required in place of the M protein criteria In addition to the above criteria, if present at baseline, a ≥50% reduction in the size of soft tissue plasmacytomas is also required. 	
Stable disease (SD)	Not meeting criteria for CR, VGPR, PR, or progressive disease	

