Blood and 24-hour urine samples will be collected as specified in the Time and Events Schedule until the development of confirmed disease progression. After subjects have completed 24 months of study treatment, the timing of collection for SPEP and UPEP (and the timing of collection of FLC for subjects with light chain multiple myeloma) will change from every 4 weeks to every 8 weeks. Disease progression based on 1 of the laboratory tests alone must be confirmed by at least 1 repeat investigation performed at least 1 day later. Disease evaluations will continue beyond relapse from CR until disease progression is confirmed. Serum and urine immunofixation test and serum free light chain assay will be performed at Screening and thereafter when a CR is suspected (when serum or 24-hour urine M-protein electrophoresis [by SPEP or UPEP] are 0 or nonquantifiable) or maintained. However, for subjects with light chain multiple myeloma, serum free light chain assay will be performed routinely. Serum immunofixation (IFE) assay samples will be split into 2 aliquots, with 1 reserved for potential follow-on testing if daratumumab interference with IFE is suspected. As daratumumab is a monoclonal IgG antibody, additional serum samples may be utilized to monitor for potential daratumumab interference with the IFE.

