1.2. Clarifications and Modifications

In order to allow these rules to be applied consistently and to be programmed, the Sponsor has added certain clarifications and modifications for using the IMWG criteria.

- **1.2.1.** Measurable disease is defined in the protocol by at least one of the following measurement: (1) serum M-protein $\geq 1 g/dL$ ($\geq 10 g/L$) or $\geq 0.5 g/dL$ ($\geq 5 g/L$) for subjects with IgA, IgD, IgE or IgM multiple myeloma; (2) urine M-protein ≥ 200 mg/24h; (3) serum FLC assay: involved FLC level ≥ 10 mg/dL (≥ 100 mg/L) provided serum FLC ratio is abnormal.
- **1.2.2.** The reference point for calculating increase and % of increase for M-protein, FLC and bone marrow plasma cells will be the lowest response value and the "lowest response value" does not need to be a confirmed value.
- **1.2.3.** Requires 2 consecutive (i.e., no intermediate values that do not meet the definition of PD) assessments made at any time before the institution of any new therapy (i.e., subsequent anti-cancer therapy). If a subject has an unconfirmed PD

followed by death due to PD within 30 days of unconfirmed PD, or PD (the same parameter as of initial observed PD) observed within 4 weeks after start of subsequent anti-cancer therapy, the unconfirmed PD will be considered as PD.

- **1.2.4.** If nadir serum M-protein is $\geq 50g/L$ ($\geq 5 \text{ g/dL}$), M-protein increases of $\geq 10g/L$ (1g/dL) is sufficient for progressive disease. It does not require meeting "increase of $\geq 25\%$ in the level of serum M-protein".
- **1.2.5.** Any 2 consecutive increase of serum M-protein \geq 5 g/L (\geq 0.5 g/dL) is consistent with progressive disease, assuming that increase of \geq 25% is met or not applicable, even if the serum M-protein level is below measurable disease threshold.
- **1.2.6.** The baseline value for assessing disease progression is the last pretreatment measurement (it applies to SPEP, UPEP, FLC, plasmacytomas and bone lesions except as noticed in Section 1.2.10). For example, if there is a screening value and a Cycle 1 Day 1 value (prior to start of treatment) for M-protein, the program ignores the screening value and uses Cycle 1 Day 1 as the reference point for assessing PD for the first post-treatment results.
- **1.2.7.** The program disregards serum M-protein and urine paraprotein measurements prior to Day 5 after dosing. These tests are considered too soon after dosing to be regarded as legitimate on-treatment values.

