- **1.2.14.** Hypercalcemia will be based on corrected calcium values as long as they are available (i.e., corrected calcium values are collected or serum calcium and albumin are collected). If corrected calcium values are not available, free-ionized calcium values will be used if they are available. Hypercalcemia based on free-ionized calcium will be defined as >1.5 mmol/L.
- **1.2.15.** For subjects who have hypercalcemia at baseline, the program will never assess PD due to "development of hypercalcemia". A subject is considered to have hypercalcemia at baseline if he or she meets one of the following criteria:
 - For subjects with corrected calcium values, any corrected calcium value >ULN which occurs on or before Day 4 (relative to first dose).
 - Note: if subject had central and local assessments done on the same day, the central record takes precedence.
 - b. For subjects without corrected calcium values in all visits, but with free-ionized calcium values on or before Day 4, any free-ionized calcium value >ULN which occurs on or before Day 4 (relative to first dose).
- **1.2.16.** For subjects with normal calcium at baseline, if the first PD criteria met is a post-baseline hypercalcemic value, then the following programming algorithm will be applied:
 - a. The program will first search for evidence of progression in other parameters within the following 56 days. If PD is determined in other parameters within the following 56 days, then the subject is assessed as PD. The date of PD is the date of the initial

- hypercalcemic value and hypercalcemia is indicated as the reason or one of the reasons for PD.
- b. If PD is not determined in other parameters within 56 days, the program will search for the next available corrected calcium/free-ionized calcium value. If the second value also meets the criteria for hypercalcemia, the subject is assessed as PD. The date of PD is the date of the initial hypercalcemic value and hypercalcemia is indicated as the reason or one of the reasons for PD.
- If there is no more follow-up calcium value, then the subject is assessed as PD.
- d. Any PD identified through a), b) or c) will be flagged and reviewed by clinical to ensure that hypercalcemia can be attributed solely to the plasma cell proliferative disorder. Hypercalcemia due to other reasons will not be considered as PD in the algorithm.

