- **1.2.17.** Descriptive (or non-numeric) results from bone marrow aspirate or bone marrow biopsy will be given a numeric interpretation based on the following conventions:
 - a. Percentage plasma cells reported as a range on the CRF page will be assigned the mean value (i.e., lower range plus upper range divide by 2) that will be analyzed by the programming algorithm (e.g., an amount reported as 10-15% would be interpreted as 12.5%).
 - b. Percent plasma cells reported as <x% will be interpreted as (x-1)% and percent plasma cells reported as >x% will be interpreted as x%.
 - c. Other conventions include:

Reported as: Interpreted as: "Not significantly present" 4% "Sheets of plasma cells not seen" 4%

- **1.2.18.** Imputation of UPEP and SPEP values: If the serum immunofixation result is "Not Detected" and the SPEP value is missing or not done, then SPEP value is treated as 0. If the urine immunofixation is "Not Detected" and the UPEP is missing or not done, then UPEP value is treated as 0.
- 1.2.19. a. Spurious UPEP values are not used in the determination. Determination of a spurious value is as follows: If at least 4 values exist in the neighborhood (+/- 94 days) of the value of interest, the mean and standard deviation of the values is computed (not including the value of interest in the calculation). The value of interest is compared to the mean +/- 3 standard deviations. If the value < mean-3*standard deviation or the value > mean+3*standard deviation then the value is considered spurious. The last two values available for a particular subject

are never considered as spurious. The baseline value for a subject is also never considered as spurious.

- b. If the first PD criteria met is two consecutive UPEP values and subject has started subsequent anticancer therapy, this subject is assessed as PD and date of PD is the date of first UPEP assessment. Otherwise, if the first PD criteria met is two consecutive UPEP values and subject has not started subsequent anticancer therapy, then the following programming algorithm will be applied:
 - The program will first search for evidence of progression in other parameters within the following 94 days. If PD is determined in other parameters within the following 94 days, then the subject is assessed as PD. The date of PD is the date of the initial UPEP value.
 - If PD is not determined in other parameters within 94 days and no more UPEP values are available, then the subject is assessed as PD due to UPEP.

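### After year 2 the spurious-urine filter does not operate on scheduled 8-weekly visits, so one spuriously low UPEP value can become the nadir and produce a false progression

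*SAP*

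**What the plan says.** SAP 4.2 bases primary PFS on a computerized algorithm, which is set out in SAP Attachment 2. The rules that matter here are:

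- **Outlier filter (1.2.19 a).** A UPEP value is tested only under the condition "If at least 4 values exist in the neighborhood (+/- 94 days) of the value of interest", not counting the value itself. Then: "The value of interest is compared to the mean +/- 3 standard deviations". A value outside those limits is dropped. The baseline value and the last two values are never dropped.
- **Reference for an increase (1.2.2).** It is the lowest value, which "does not need to be a confirmed value".
- **Size of a urine progression (1.1.1 b).** The rise must be at least 25% and at least 200 mg/24 h.
- **Confirmation (1.2.3).** "Requires 2 consecutive (i.e., no intermediate values that do not meet the definition of PD) assessments made at any time before the institution" of new therapy. Where UPEP alone triggers progression and no new therapy has started, 1.2.19 b looks for progression in other parameters within 94 days, then at the third UPEP value, then at the fourth. If no further UPEP value exists, two suffice.

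Protocol 9.2.1.1 sets the schedule: "Disease evaluations must be performed every 28 days for the first 2 years and then every 8 weeks until disease progression", with this tolerance: "A window of ± 7 days is allowed". Protocol 9.2.1.2 applies the same change to UPEP collection after 24 months of treatment: it "will change from every 4 weeks to every 8 weeks". Nothing in Attachment 2 adapts the 94 days to the longer interval.

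**The concern.** The 94 days equal three 4-week intervals plus 10 days (3 × 28 + 10), so the filter appears to have been designed for the first two years. If the window stays fixed while the interval doubles, the same urine pattern is cleaned out in year 2 and left in during year 3.

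The unconfirmed nadir makes this consequential. The confirmation rules test whether an increase persists. They do not test whether the low point it is measured from was real. If that low point is an artefact, every later ordinary value confirms the error. What is at stake is the date or status of progression in algorithm-based PFS and TTP for subjects followed past month 24.

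**Working it through.** **1. How many neighbours the schedule supplies.** Inputs: the 94-day window (SAP Attachment 2, 1.2.19 a), and 28-day then 56-day intervals with a 7-day tolerance either way (Protocol 9.2.1.1). The tolerance can change the distance between two visits by up to 14 days.

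- 4-weekly: neighbours at 28, 56 and 84 days on each side, so 6. Under all allowed visit shifts the count is 5 or 6.
- 8-weekly: neighbours at 56 days on each side, so 2. The next lie at 112 days, and at least 112 − 14 = 98 days away, which is beyond 94. The count is 2 under every allowed shift.

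Across the switch (assuming 28-day visits to day 728, then 56-day visits, on nominal dates):

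| Day of value | Other values within 94 days | Filter can act |
|---|---|---|
| 672 | 5 | yes |
| 700 | 5 | yes |
| 728 | 4 | yes |
| 784 | 3 | no |
| 840 onward | 2 | no |

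One unscheduled urine inside the window restores the count at day 784. Two are needed later.

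**2. A low value worked through the rules.** Take a subject stable at 300 mg/24 h with one spurious value of 50.

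- *4-weekly.* With an assumed coefficient of variation (CV) of 10 to 20%, the neighbours have an SD of about 30 to 60. The lower limit is 300 − 3 × 30 = 210, or 300 − 3 × 60 = 120. The value 50 lies below both and is dropped.
- *8-weekly.* There are two neighbours, so no test is made, and 50 becomes the nadir. The next value of 300 is a rise of 250 mg/24 h (at least 200) and of 250/50 = 500% (at least 25%). The one after it meets 1.2.3. The third UPEP value, again 300, meets 1.2.19 b. The program records progression.

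**3. A high value worked through the same rules.** One value of 900 against a stable 300 meets the size criterion once. The next value, 300, does not, so 1.2.3 is not met. In 2,000 simulated 8-weekly series (SD 15), one high value gave progression in 0%. Two consecutive high values followed by normal ones also gave 0%, because of the third- and fourth-value checks.

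**4. Simulation of the low value.** The urine levels and variability are assumptions; the documents give none. With a residual of 300, one value of 50, lognormal variation with CV 10 to 20%, and visits shifted by up to 7 days:

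| Schedule and window | False progression |
|---|---|
| 4-weekly, 94 days | 0 to 8% |
| 8-weekly, 94 days | 93 to 99.8% |
| 8-weekly, 178 days | 0 to 8% |

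With a stable residual of 150 the result is 0% even for a bad value of 0, because a rise of 200 mg/24 h is out of reach.

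**5. When it could first happen.** The earliest unprotected scheduled value is at about day 784. Two further 8-weekly values bring it to about day 784 + 112 = 896, or roughly month 29. Under the plan's assumptions (medians of 24 and 24/0.75 = 32 months, uniform accrual over 21 months, 365 per arm, 5% annual dropout), 234 events are reached at about month 27. About 2 of them (0.8%) fall after a subject's month 24.

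**The case against.** The strongest reply is that the exposed subject is unusual. The true UPEP must be at least 200 mg/24 h above the bad value, so anyone stable below 200 is immune. A stable 300 meets the urine part of PR only through the 90% reduction, which needs a baseline of at least 3,000. Otherwise the subject is an unprogressed urine non-responder beyond two years. The simulated percentages are conditional on this constructed case. All of this stands, and it limits how many subjects can be affected.

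Several stronger readings are tempting, and the documents do not support them:

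- *Any single bad urine value can create a PFS event.* Not a high one: the two-consecutive rule and the third- and fourth-value checks do not depend on visit spacing.
- *The filter can never operate after year 2.* Unscheduled urines can restore it. Protocol 9.2.1.2 calls for a repeat when progression rests on one laboratory test alone.
- *The other fixed windows share the fault.* For hypercalcemia, 1.2.16 a says: "The program will first search for evidence of progression in other parameters within the following 56 days". It then falls through to the next calcium value and to clinical review. The 94-day search in 1.2.19 b falls through to the third and fourth UPEP values. On 8-weekly visits these windows span fewer assessments, but they are not disabled.
- *The error favors one arm.* The plan's assumptions leave 0.50 × 0.95² = 45% of Rd and 0.595 × 0.95² = 54% of DRd subjects at risk at month 24. The relevant denominator, however, is unprogressed subjects with high residual urine protein, and no figure for that exists by arm.
- *A fifth of primary PFS events are exposed.* The 19 to 21% of events after month 24 belongs to the planned 390-event analysis, which the interim planned at 234 events replaced.

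Two further objections carry weight. After Amendment 8, evaluations follow local practice (Protocol 9.1.6), so later visits may not be 8-weekly. Changing the program once results are known, in an open-label trial, also invites suspicion. Both argue for showing the two window definitions side by side rather than for leaving the rule alone. Investigator-assessed PFS (SAP 4.2.3.1) is a partial check.

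**Conclusion.** The concern holds in a limited form. On scheduled 8-weekly visits the filter's entry condition cannot be met; this follows from the stated schedule and window alone. A single spuriously low urine value can then become an unconfirmed nadir and turn stable disease into confirmed progression.

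The near-certain false progression in the 8-weekly simulation describes one constructed subject (300 mg/24 h, one value of 50, CV 10 to 20%). It is not a rate in the trial. Exposed subjects are probably few, and the documents give neither their number nor their split by arm.

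The effect falls mainly on follow-up beyond month 24, that is, on the final CSR update of PFS and TTP planned about 5 years after the last randomization. No effect on the primary PFS analysis is shown. Under the plan's assumptions the route could not have completed by the 234th event. Actual follow-up at the 24 September 2018 cut-off is not stated and may have been longer.

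**What to change.** In SAP Attachment 2, 1.2.19 a, define the neighbourhood in scheduled evaluation intervals: 3 intervals plus 10 days. This keeps 3 × 28 + 10 = 94 days on 4-weekly visits and gives 3 × 56 + 10 = 178 days on 8-weekly visits. Securing four neighbours under every allowed shift needs at least 112 + 14 = 126 days, so 178 is enough. The SAP already scales a rule this way: the missed-evaluation sensitivity analysis in 4.2.3.3 uses 2.5 evaluation intervals.

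Re-run algorithm-based PFS and TTP for the final CSR with the revised window, and report the 94-day result alongside so that any change is visible. Leave the 56-day hypercalcemia window and the 94-day look-ahead in 1.2.19 b as they are.

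The cost is a wording change, a program change and re-validation, with no new data. A few progression dates or statuses may change.

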Progressive disease (PD) [†]	 Increase of 25% from lowest response value in any one of the following: Serum M component (absolute increase must be ≥0.5 g/dL), Urine M component (absolute increase must be ≥200 mg/24 hours), Only in subjects without measurable serum and urine M protein levels: the difference between involved and uninvolved FLC levels (absolute increase must be >10 mg/dL) Definite development of new bone lesions or soft tissue plasmacytomas or definite increase in the size of existing bone lesions or soft tissue plasmacytomas Development of hypercalcemia (corrected serum calcium >11.5 mg/dL) that can be attributed solely to the PC proliferative disorder 	

FLC free light chain; PC plasma cell

All response categories (CR, sCR, VGPR, PR, and PD) require 2 consecutive assessments made at any time before the institution of any new therapy; CR, sCR, VGPR, PR, and SD categories also require no known evidence of progressive or new bone lesions if radiographic studies were performed. VGPR and CR categories require serum and urine studies regardless of whether disease at baseline was measurable on serum, urine, both, or neither.

Radiographic studies are not required to satisfy these response requirements. Bone marrow assessments need not be confirmed. For PD, serum M component increases of more than or equal to 1 g/dL are sufficient to define relapse if starting M component is ≥ 5 g/dL.

- * Clarifications to IMWG criteria for coding CR and VGPR in subjects in whom the only measurable disease is by serum FLC levels: CR in such subjects indicates a normal FLC ratio of 0.26 to 1.65 in addition to CR criteria listed above. VGPR in such subjects requires a >90% decrease in the difference between involved and uninvolved FLC levels.
- † Clarifications to IMWG criteria for coding PD: Bone marrow criteria for PD are to be used only in subjects without measurable disease by M protein and by FLC levels; "25% increase" refers to M protein, FLC, and bone marrow results, and does not refer to bone lesions, soft tissue plasmacytomas, or hypercalcemia and the "lowest response value" does not need to be a confirmed value.
- ^a Presence/absence of clonal cells is based upon the kappa/lambda ratio. An abnormal kappa/lambda ratio by immunohistochemistry or immunofluorescence requires a minimum of 100 plasma cells for analysis. An abnormal ratio reflecting presence of an abnormal clone is kappa/lambda of >4:1 or <1:2.

Clinical Relapse

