 - 3) Otherwise, the third UPEP value is considered. If the third value meets the criteria for PD, the subject is assessed as PD due to UPEP. If the third value does not meet the criteria for PD, but other parameters indicate PD within the next 94 days, the subject is assessed as PD due to UPEP at the time of the initial UPEP value.
 - 4) Otherwise, the fourth UPEP value is considered. If the fourth value meets the criteria for PD, the subject is assessed as PD due to UPEP. If the fourth value does not meet the criteria for PD, the subject is not assessed as PD due to UPEP. If no fourth UPEP value is available, the subject is not assessed as PD.
- **1.2.20.** Difference between involved and uninvolved FLC level is defined as absolute value of kappa FLC level minus lambda FLC level in the serum.
- **1.2.21.** Development of plasma cell leukemia is considered as disease progression. The date of PD is the date of event onset.

2. Determination of Date of Censoring and Reason for PD

The date of last post-baseline efficacy measure is used as the censoring date for all subjects without progressive disease. Subjects that have no post-baseline efficacy data are censored at the date of randomization for randomized subjects.

The reason(s) for PD is defined as the initial reason(s) that caused the program to indicate PD as well as any other criteria that were met by the time of confirmation of PD. Indicator variables for each reason (SPEP, UPEP, FLC, bone marrow, bone lesion [increase in number, increase in size], extramedullary plasmacytoma [new extramedullary plasmacytoma, increase in size], hypercalcemia and plasma cell leukemia) are created.

3. Determination of Response Category and Duration of Response

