3.1.3. Definition of VGPR

Requires any of the following:

a. Serum and urine M-component detectable by immunofixation but not on electrophoresis (3.2.5; 3.2.11;3.2.12), or

- b. \geq 90% reduction $^{(3.2.10)}_{(3.2.5; 3.2.11)}$ in serum M-protein plus urine M-protein \leq 100 mg/24 hours $^{(3.2.5; 3.2.11)}$
- c. If the serum and urine M-protein are not measurable, a reduction (3.2.10) of >90% in the difference between involved and uninvolved FLC levels (3.2.5; 3.2.13) is required.
- d. In addition to the above criteria, if present at baseline, ≥50% reduction ^(3.2.10) in the size of soft tissue plasmacytomas is also required.

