3.2. Clarifications and Modifications

As was the case with PD, developing a program to assess response requires adding certain clarifications, minor modifications and additions to the IMWG criteria.

- **3.2.1.** Only subjects with measurable disease at baseline are eligible for assessment of response (i.e., considered in the response-evaluable population). Measurable disease is defined in Section 1.2.1; only legitimated on treatment serum M-protein and urine paraprotein measurements are used for assessment of response. The legitimated on treatment measurements is defined in Section 1.2.6.
- **3.2.2.** CR, sCR, VGPR, PR, MR and SD response categories require no known evidence of progressive or new bone lesions if radiographic studies were performed. Once the program has determined PD for a subject, no subsequent response assessments are performed. For example, a subject who progresses at week 6 cannot have a first response or best response that starts after week 6.

- **3.2.3.** Subjects with measurable disease (defined in Section 1.2.1) in serum (SPEP) and urine (UPEP) need to be followed by both SPEP and UPEP for response assessment and categorization; Except for assessment of CR or better, subjects with measurable disease restricted to the SPEP will need to be followed only by SPEP (i.e., urine M-protein need not show a reduction, but the available urine M-protein values must not meet the criteria for PD); correspondingly, subjects with measureable disease restricted to the UPEP will need to be followed only UPEP (i.e., serum M-protein need not show a reduction, but the available serum M-protein values must not meet the criteria for PD). For example, a subject who has baseline values of 0.1 g/dL of IgG M-protein and 300 mg/24 hrs of urine paraprotein and who subsequently maintains values of 0.1 g/dL and 120 mg/24 hrs will be regarded as achieving a PR; Subjects with measurable disease in either SPEP or UPEP or both will be assessed for response only based on these two tests and not by the FLC assay.
- **3.2.4.** To be considered CR, both serum and urine immunofixation must be carried out and be negative regardless of the size of baseline M-protein in the serum or urine; subjects with negative UPEP values pretreatment still require UPEP testing to confirm CR.

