- **3.2.5.** Requires 2 consecutive (i.e., no intermediate values that do not meet the definition of response) assessments made at any time before the institution of any new therapy (i.e., subsequent anti-cancer therapy).
- **3.2.6.** For coding CR in subjects in whom the only measurable disease is by serum FLC levels: it requires a normal FLC ratio (Kappa/Lambda) in addition to CR criteria. However, a normal FLC ratio is not required if the involved FLC level decrease to below detectable level (Kappa<0.5 mg/L or Kappa<0.67 mg/L based on new reagent lot; or lambda<0.6 mg/L). The default reference range of 0.26 to 1.65 will be used to determine normal FLC ratio, if the reference range from central/local laboratory is not available.
- **3.2.7.** If all criteria for confirmed CR were met, except that bone marrow aspirate and biopsy were not performed, and baseline bone marrow evaluation showed <5% plasma cells, then the algorithm accepts this as a CR. If both bone marrow aspirate and bone marrow biopsy were performed at baseline, then both values must have <5% plasma cells for the rule to be applied. For subjects without measurable disease at baseline or subjects whose baseline bone marrow plasma cells percentage is >5%, bone marrow confirmation is required for CR response.

- **3.2.8.** Normal FLC ratio is required for all subjects regardless of whether disease at baseline was measurable on serum, urine, both or neither. However, a normal FLC ratio is not required if the involved FLC level decrease to below detectable level (Kappa<0.5 mg/L or Kappa<0.67 mg/L based on new reagent lot; or lambda<0.6 mg/L). The default reference range of 0.26 to 1.65 will be used to determine normal FLC ratio (Kappa/Lambda), if the reference range from central/local laboratory is not available.
- **3.2.9.** Presence/absence of clonal cells is based upon the kappa/lambda ratio. An abnormal kappa/lambda ratio by immunohistochemistry or immunofluorescence requires a minimum of 100 plasma cells for analysis. An abnormal ratio reflecting presence of an abnormal clone is kappa/lambda of >4:1 or <1:2.
- 3.2.10. Reductions are based on changes from baseline.

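### The algorithm codes involved-minus-uninvolved FLC as |kappa − lambda|, which departs from Protocol Table 8 once the uninvolved chain exceeds the involved one and can misclassify response, and rarely progression, in FLC-only subjects

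*SAP*

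**What the plan says.** Protocol Table 8 (Section 9.2.1.1) bases FLC assessment on a difference with a direction. For progression, in subjects without measurable serum and urine M-protein, the quantity is "the difference between involved and uninvolved FLC levels (absolute increase must be >10 mg/dL", with a 25% rise also needed. For response in subjects measurable only by FLC, "VGPR in such subjects requires a >90% decrease in the difference between involved and uninvolved FLC levels"; PR needs a fall of at least 50% in the same difference.

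SAP Attachment 2 carries the same criteria in items 1.1.1c (PD), 3.1.3c (VGPR, a reduction "in the difference between involved and uninvolved FLC levels") and 3.1.4b (PR). It then gives the programming definition, identically in 1.2.20 and 3.2.13: "Difference between involved and uninvolved FLC level is defined as absolute value of kappa FLC level minus lambda FLC level in the serum".

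The surrounding rules are:
- **PD reference (1.2.2):** "The reference point for calculating increase and % of increase for M-protein, FLC and bone marrow plasma cells will be the lowest response value".
- **PD confirmation (1.2.3):** "Requires 2 consecutive (i.e., no intermediate values that do not meet the definition of PD) assessments".
- **Response reference (3.2.10):** "Reductions are based on changes from baseline".
- **Scope (3.2.3):** "Subjects with measurable disease in either SPEP or UPEP or both will be assessed for response only based on these two tests", so FLC does not enter response for them.

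**The concern.** The absolute value discards which chain belongs to the clone. Once the involved chain falls below the uninvolved one, a further fall in the clone or a rise in the normal chain makes the programmed measure larger. The algorithm reads that as a weaker response or as an increase from nadir. Table 8 would read it as further improvement.

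Nothing else in Attachment 2 catches this. UPEP has a spurious-value screen and extra confirmation steps (1.2.19), and hypercalcemia-based PD goes to clinical review (1.2.16d). FLC-based PD has neither, and no rule asks which chain rose.

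The algorithm determines primary PFS (SAP 4.2). It also determines VGPR or better and ORR, which stand second and fourth in the hierarchical testing order (SAP 4.1.1). FLC-only subjects are eligible under inclusion criterion 2.1 and form a named baseline category (SAP 3.1).

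**Working it through.** The plan states no figure on this point, so the check applies both definitions to the same values. All FLC values below are illustrations in mg/dL.

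**1. Where the definitions part.** Let i be involved FLC, u uninvolved FLC, d = i − u (Table 8) and a = |i − u| (SAP). If i ≥ u, then a = d, and a rise in u lowers both equally. If i < u, then a = u − i = −d, and the two move in opposite directions.

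**2. Response at a visit.** Let d0 be the baseline difference. VGPR needs 1 − a/d0 > 0.90. After crossing it therefore fails when u − i ≥ 0.10 × d0. PR needs 1 − a/d0 ≥ 0.50, so it fails when u − i > 0.50 × d0.

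Example, kappa disease: baseline 12.0/0.8 gives d0 = 11.2; on treatment the values are 0.3/1.8.
- SAP: a = 1.5, and 1 − 1.5/11.2 = 86.6%. VGPR is not met.
- Table 8: d = −1.5, and 1 + 1.5/11.2 = 113.4%. VGPR is met.

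| Baseline difference | VGPR fails at excess ≥ | PR fails at excess > |
|---|---|---|
| 3.94 | 0.39 | 1.97 |
| 7.4 | 0.74 | 3.7 |
| 11.2 | 1.12 | 5.6 |
| 14.5 | 1.45 | 7.25 |
| 50 | 5 | 25 |
| 100 | 10 | 50 |

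The first two rows are about the smallest baseline differences that the 10 mg/dL entry threshold allows: 10 − 10/1.65 = 3.94 (kappa disease) and 10 − 0.26 × 10 = 7.4 (lambda disease).

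**3. From a failed visit to a lost response.** Two routes can rescue the subject.
- *CR.* VGPR or better includes CR (SAP 4.3.2.1), and CR does not use the difference. Item 3.2.6 asks for a normal ratio (default 0.26 to 1.65) or an undetectable involved chain, plus the other CR criteria. At 0.5/1.8 the excess of 1.3 fails VGPR by FLC (1 − 1.3/11.2 = 88.4%), but the ratio is 0.28 and CR stays open. At 0.3/1.8 the ratio is 0.17 and kappa is 3 mg/L, above the 0.5 or 0.67 mg/L detection limit, so CR is closed at that visit.
- *Earlier visits.* Response counts at any time and needs two consecutive assessments (3.2.5). Evaluations are every 28 days for two years. A subject with two consecutive values of a below 1.12 before the excess grew keeps VGPR.

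**4. Progression.** PD needs a rise from nadir of more than 10 mg/dL and at least 25%, on two consecutive assessments.
- Lambda disease, nadir lambda 1.5 and kappa 1.4 (a = 0.1); later lambda 1.5 and kappa 12.0 (a = 10.5). The SAP increase is 10.4, which is PD if repeated. Under Table 8, d goes from 0.1 to −10.5, so there is no PD.
- A smaller rise does not trigger it. With involved 0.5 and uninvolved 0.4 at nadir (a = 0.1), then uninvolved 9.0 and 9.5, a is 8.5 and 9.0, and the increases are 8.4 and 8.9.

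**5. The opposite error.** Take involved/uninvolved 15/0.5, 0.3/3.3, 9.0/1.0, 9.2/1.0. The SAP nadir is 3.0 and the increases are 5.0 and 5.2, so no PD. With an unfloored signed difference the nadir is −3.0 and the increases are 11.0 and 11.2, so PD. With a floor at 0 the increases are 8.0 and 8.2, so no PD. The absolute rule thus understates a true relapse by the uninvolved excess at nadir (3.0 here) relative to a floored rule. A correction must therefore say how negative values are handled.

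**The case against.** The strongest defence is about reach.
- The rule touches only FLC-only subjects, and only after the chains cross.
- The 11.2 example lies near the entry threshold. At a baseline difference of 100, VGPR fails only at an excess of 10 mg/dL.
- The PD example has a kappa/lambda ratio of 8 (12.0/1.5) with a chain above the trial's own 10 mg/dL measurability threshold. The documents do not establish that such a value is benign.
- SAP Section 4 says the algorithm was validated by an independent review committee in another study. Investigator-assessed sensitivity analyses are planned for PFS (4.2.3.1) and response (4.3.1.2).
- The primary PFS analysis is complete.

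All of this limits the size; none of it reconciles the two definitions. The investigator analyses replace the whole assessment source, so they neither isolate this rule nor correct the algorithm.

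Three stronger readings are tempting and are not supported:
- A reader might infer that any excess above the threshold costs the subject VGPR. The CR route and earlier qualifying visits contradict that.
- A reader might infer that the PFS result is unsafe. The confirmed excess of more than 10 mg/dL over nadir makes false PD hard to reach, and nothing in the documents shows that it occurred.
- A reader might infer bias between arms because the regimens could suppress normal plasma cells differently. The documents give no data on this.

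**Conclusion.** Items 1.2.20 and 3.2.13 are wrong as written: they do not implement the involved-minus-uninvolved criterion of Table 8 or of the SAP's own items 1.1.1c, 3.1.3c and 3.1.4b.

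The main practical effect is on VGPR, at visits where the uninvolved excess reaches 10% of the baseline difference. The effect on PR, and so ORR, needs more than 50%. False PD is possible but should be rare. CR or better and MRD negativity do not use the difference.

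The number affected cannot be determined. The documents give neither the FLC-only share nor the frequency of crossing. If the share were 3% to 10% (an assumption), 0.03 × 730 ≈ 22 to 0.10 × 730 = 73 subjects would come under the rule, and only those whose chains cross could be misclassified. The defect should be corrected; it does not by itself call the trial's conclusions into question.

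**What to change.** In both 1.2.20 and 3.2.13, define the difference as involved FLC minus uninvolved FLC, with the involved chain fixed per subject from the abnormal baseline kappa/lambda ratio, and floor the difference at 0. State two conventions:
- For response, a value of 0 counts as a 100% reduction.
- For PD from a nadir of 0, the 25% condition is taken as met and the absolute increase of more than 10 mg/dL governs.

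Under this rule the 12.0/0.8 to 0.3/1.8 subject meets the FLC criterion for VGPR, and the lambda subject in the PD example has a floored difference of 0 and no PD.

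Re-run the algorithm for FLC-only subjects and list those whose classification changes. Report PFS, VGPR or better and ORR under the corrected definition as a supplementary analysis alongside the results under the current SAP rule. The final CSR analysis, which updates efficacy (Protocol 3.1), is a natural place. If nothing changes, one sentence can say so.

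The cost is a small amount of reprogramming and revalidation. No new data are needed: kappa, lambda and the baseline ratio are collected, and the algorithm already uses the involved chain in 1.2.1, 3.2.6 and 3.2.8.
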